## **1.Integrity statement**

This study ensures that the operation is strictly in accordance with the test procedures and the authenticity of the data records; there is no conflict of interest in this study.

## **2. Research topic**

External diaphragm pacing therapy and correlation study on trunk balance and respiratory function in stroke patients

## **3. Research background:**

Stroke is a common neurological disease in clinical practice and is the leading cause of death and disability worldwide. Post-stroke patients are often left with multiple functional impairments. Although most people return to walking independently 6 months after stroke, balance and trunk control problems persist in the chronic stage of the disease, which has a significant impact on patients' quality of life. Impact. Post-stroke patients not only have functional impairments in limb movement and balance, but their respiratory function is also significantly lower than that of normal people. Clinical studies report that respiratory muscle training can not only improve respiratory function, but also promote the recovery of the body's balance function and trunk control ability. Some studies have pointed out that human trunk control also involves interaction with key respiratory muscles. When the activation of respiratory muscles is damaged, core stability decreases, affecting normal trunk balance. However, the correlation between trunk balance ability and respiratory function in stroke patients has not yet been clarified, which may provide new ideas for clinical rehabilitation evaluation and treatment of stroke patients.

[figure not shown]
There are many clinical methods to evaluate the respiratory function of stroke patients. The commonly used quantitative evaluation methods are pulmonary ventilation function assessment and diaphragm ultrasound imaging. The diaphragm is the main respiratory muscle of the human body. Extracorporeal diaphragm pacing ( EDP ) therapy applies neuromuscular electrical stimulation of appropriate intensity and frequency to the phrenic nerve, which can improve the patient's respiratory movement by affecting the passive activity of the diaphragm and is beneficial to the treatment. Respiratory muscle weakness has significant effects. At present, clinical studies mostly use EDP for pulmonary function rehabilitation in patients with central nervous system diseases. It is believed that it can enhance the strength of respiratory muscles and improve patients' breathing exercises and quality of life. Studies have pointed out that EDP can not only improve the respiratory function of stroke patients, but also enhance trunk control ability. However, such reports are rare and limited to clinical observations. There are few studies on EDP's promotion of trunk balance function recovery and its specific mechanism of action. Based on this, the purpose of this study is to apply EDP to treat stroke patients, observe the improvement of trunk balance ability, lung function and

diaphragm function in stroke patients, and analyze the correlation between trunk balance ability and respiratory function indicators.

#### 4. Research purpose

Apply EDP to treat stroke patients, observe the improvement of trunk balance ability, lung function and diaphragm function in stroke patients, and analyze the correlation between trunk balance ability and respiratory function indicators.

#### 5. Design plan

#### 6. Research matters execution process

2023.01.01 to 2023.08.01 , and relevant data before and after the intervention will be entered and sorted. Continue to review relevant domestic and foreign literature related to this topic and make a summary.

2023.08.02-2023.09.30 The first stage of data analysis, discussion of results, and writing of the paper.

2023.09. 3 0-2024.09.30 Continue to recruit subjects , conduct second-stage data analysis, discuss results, and write papers .

#### 7. Recruitment of participants

30 stroke patients admitted to the Department of Rehabilitation Medicine of the First Affiliated Hospital of Anhui Medical University from January 2023 to August 2023 were randomly selected in the first phase .

#### 8. Ethical considerations

This study has been approved by the Ethics Committee of the First Affiliated Hospital of Anhui Medical University. In accordance with the ethical principles of the "Ethical Review Methods for Biomedical Research Involving Humans", WMA's "Declaration of Helsinki" and CIOMS's "International Ethical Guidelines for Biomedical Research Involving Humans", after review and approval by the chief review committee, the review results will be reported to the ethics committee. Agree It carried out this research and published the research results publicly. Approval time is September 20, 2023, approval number: PJ2023-11-49.

## **9. Inclusion and exclusion criteria**

Inclusion criteria: ①Patients who meet the diagnostic criteria for stroke for the first time; ②Patients whose disease duration is within 6 months, have received specialist and standardized treatment, and have stable vital signs; ③are informed of this study, voluntarily accept rehabilitation treatment, and sign an informed consent form; ④no chronic breathing before and after stroke History of systemic and circulatory diseases. ⑤ The patient can maintain the starting posture evaluated by the mTIS scale for 10 seconds. The standard for the starting posture is: sitting on the edge of the bed without any support for the back and arms, with the thighs in full contact with the bed surface, and with the feet flat and the same width as the hips. On the ground, bend your knees 90° and place your arms on your thighs.

Exclusion criteria: ① People with severe heart, lung and other organ function diseases, such as pulmonary embolism, pacemaker placement, etc.; ② People with severe cognitive impairment and abnormal hearing and understanding; ③ People who are not suitable for electrical stimulation treatment Other reasons include sudden instability of vital signs, malignant tumors, combined mental illness, etc.

## **10. Grouping method**

Eligible patients were recruited by members of the project team and divided into experimental groups and control groups through a random number table method . Subjects were randomly enrolled and were unaware of their grouping , and only some researchers were informed of the grouping .

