## **12. Measurement indicators**

(1) Pulmonary function measurement: Use an exercise cardiopulmonary testing system (Nanjing Hanya Smax58ce) to test the patient's lung function before treatment and 4 weeks after treatment, including forced vital capacity (FVC), forced expiration in 1 second Forced Expiratory Volume in 1 second (FEV1), FEV1/FVC (%), standing and supine vital capacity (Position vital capacity, VC), and calculate the change percentage of vital capacity from standing to supine position  $[\Delta VC (\%) : (upright vital capacity - supine vital capacity) / supine vital capacity (\%)]$ .

(2) Diaphragm function evaluation: The American Sonosonic portable color ultrasound (M-Turbo) was used to measure the diaphragmatic excursion of quiet breath (DE-QB) on the hemiplegic side of the two groups of patients before treatment and 4 weeks after treatment. and forced breathing diaphragm mobility (Diaphragmatic excursion of deep breath, DE-DB), and measure the thickness of the hemiplegic side diaphragm (The thickening of the diaphragm, Tdi) at the end of expiration and end of inhalation to calculate the diaphragm thickening rate [Thickening fraction, TF: (diaphragm thickness at end-inspiration - diaphragm thickness at end-expiration) / diaphragm thickness at end-expiration (%)].

(3) The Modified Trunk Impairment Scale to Norwegian Version ( mTIS ) is used to evaluate the patient's trunk balance ability before treatment and after 4 weeks of treatment.

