#### **14. Statistical analysis methods**

All data were analyzed using spss26.0, count data were expressed as frequencies, and Fisher's exact probability method was used; for measurement data that conformed to normal distribution, the independent sample t test was used for comparison between groups, and Pearson correlation analysis was used for correlation; if it did not conform to normality Rank sum test was used for comparison of distribution between groups, and Spearman correlation analysis was used for correlation.  $P<0.05$  was considered as a statistically significant difference.

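### No blocking, stratification or adjustment for time since stroke is stated, although entry spans durations up to 6 months and phase one has only 30 patients: valid, but imprecise and exposed to chance imbalance

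*Protocol*

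**What the plan says.** Protocol section 10 (Grouping method) describes allocation in one clause: patients are "divided into experimental groups and control groups through a random number table method". It gives no allocation ratio and no blocks or strata.

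Section 9 (Inclusion and exclusion criteria) caps disease duration at 6 months and sets no lower limit in days or weeks. It does require that patients "have received specialist and standardized treatment, and have stable vital signs" and can hold an unsupported sitting posture for 10 seconds.

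Section 7 (Recruitment of participants) gives the number: "30 stroke patients admitted to the Department of Rehabilitation Medicine", who "were randomly selected in the first phase". Section 6 (Research matters execution process) then plans to "Continue to recruit subjects , conduct second-stage data analysis", with no total stated.

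Outcomes are taken before treatment and at 4 weeks. For the trunk scale, section 12 says it is used to "evaluate the patient's trunk balance ability before treatment and after 4 weeks of treatment". Section 14 fixes the comparison: for normally distributed data "the independent sample t test was used for comparison between groups", otherwise a rank sum test. Neither test uses the baseline value or time since stroke.

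**The concern.** A 4-week gain after stroke may depend on how long ago the stroke was, whatever the arm. With few patients and no stated restriction on the list, one arm can by chance receive more recent strokes, and the arms can also end up unequal in size. The unadjusted tests have no means of separating such a difference from an effect of diaphragm pacing in the one allocation that the trial will have. A baseline trunk score or lung volume measures where a patient stands, not how fast that patient is recovering, so baseline adjustment alone need not remove the problem.

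Time since stroke has to be ascertained to apply the 6-month limit. The plan therefore already needs a variable that may be prognostic, and uses it neither in allocation nor in the stated comparison.

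**Working it through.** **Inputs from the protocol.** 30 patients in phase one (section 7); duration up to 6 months (section 9); random number table (section 10); unadjusted t test or rank sum test at 0.05 (section 14). The protocol states no effect size, SD, power or ratio, so it has no figure to reproduce.

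**Assumptions.** Two-sided test. Simple 1:1 allocation for arm size; 15 v 15 elsewhere. Half the patients early where an early/late split is used. Early patients gain 0.5 to 1.0 SD more in 4 weeks. Correlation of time since stroke with outcome (rho) 0.3 to 0.7.

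**1. Arm size.** With X ~ Binomial(30, 0.5):
- 12:18 or worse: 0.36
- 11:19 or worse: 0.20
- 10:20 or worse: 0.099

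Relative efficiency at 10:20 is 4 × 10 × 20 / 30² = 0.889, a loss of 11%.

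**2. Early/late mix.** Hypergeometric, 15 early among 30, arms of 15:
- 9 v 6 or worse: 0.466
- 10 v 5 or worse: 0.143 (both directions; about 0.07 in favour of either given arm)

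For any continuous baseline factor, the difference between arm means has SD √(2/15) = 0.365 SD units. The 95% limit is 1.96 × 0.365 = 0.72, and a difference above 0.5 SD has probability 0.17.

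**3. Effect on the group difference.** Shift = (10/15 − 5/15) × early-late gap = gap/3, so 0.5/3 = 0.17 SD to 1.0/3 = 0.33 SD. With 15 per arm, the effect detectable with 80% power is 1.06 SD (t test; 1.02 by the normal approximation). The shift is thus 0.17/1.06 = 16% to 0.33/1.06 = 31% of it. If there is no gap, there is no shift.

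**4. Error rates.** Averaged over simple allocations, the unadjusted t test with rho = 0.5 and no treatment effect rejects in 0.049 of simulated trials. Given a realised 10 v 5 split, simulated rejection under no effect is about 6.5% (gap 0.5 SD) to 10–11% (gap 1.0 SD).

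**5. Gain from using the variable.** Detectable effect = (1.96 + 0.84) × √(2/15) × √(1 − rho²):

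| rho | Detectable effect, SD |
|---|---|
| 0 | 1.02 |
| 0.3 | 0.98 |
| 0.5 | 0.89 |
| 0.7 | 0.73 |

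The 0.5 to 1.0 SD gap with half the patients early corresponds to rho of about 0.25 to 0.5, so the lower part of this range is the relevant one.

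**6. Effect of stratifying.** If durations were uniform over 0 to 6 months and balanced within two strata cut at 3 months (for illustration only), the SD of the between-arm difference in mean duration falls from 0.64 to 0.33 months, and its 95% limit from 1.25 to 0.65 months.

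**The case against.** Simple randomisation is a valid design, and the P value already allows for chance imbalance. That stands: what is at stake is precision and the reading of one realised result, not a biased test.

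A reader might infer that imbalance could rival the treatment effect. The documents do not support this. No target effect is stated, and against the roughly 1 SD that 15 per arm can detect, the chance that the shift equals it is at most about 0.0001 even at rho = 0.7. It becomes appreciable only for a small effect with a strong link: 0.10 to 0.24 for an effect of 0.3 SD with rho of 0.5 to 0.7.

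A reader might also take section 3, which begins "Although most people return to walking independently 6 months after stroke", as evidence that early patients gain faster on the trial's outcomes. The same sentence goes on to say that balance and trunk problems persist into the chronic stage, and walking is not an outcome here. The early-late gap is therefore an assumption and could be small or nil.

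Three further limits are fair:
- Section 10 is silent rather than explicit. A random number table can be used to build blocks, so the list is not shown to be unrestricted.
- The treatment, stability and sitting conditions in section 9 trim the earliest and most severe patients, so entry does not run from the moment of onset.
- Thirty is phase one only, and imbalance shrinks as recruitment continues.

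It can also be said that covariates belong in an analysis plan that is not shown. That is true of an omission. Section 14, however, names the between-group tests, and the allocation scheme has to exist before patients enter.

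**Conclusion.** The point holds as an inexpensive improvement to a valid design. The protocol states no restriction on allocation and prescribes unadjusted tests in a small first phase with a wide range of time since stroke. Arm sizes of 10:20 or worse (about 10%, if allocation was simple) and a 10 v 5 split of early patients or worse (about 14%, if half are early and arms are 15 v 15) are realistic. The second would move the group difference by 0.17 to 0.33 SD if the assumed gap is right.

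At correlations of 0.3 to 0.5, using time since stroke lowers the detectable effect from 1.02 SD to between 0.98 and 0.89 SD. This is a modest gain, but useful where power for an effect of 0.5 SD is only about 26%. The size of both the distortion and the gain rests on a link between duration and 4-week gain that the documents do not quantify.

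**What to change.** **Section 10.** State the allocation ratio and how the random number table was used for phase one, including any blocks. For all further enrolment, use a computer-generated list in permuted blocks of varying size, stratified by time since stroke in two levels, with the cut point fixed before the list is made.

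**Section 14.** At both stages, replace the unadjusted comparison with a linear model (ANCOVA) for the 4-week value, with group, the baseline value and time since stroke. This also covers the first 30 patients, whose allocation can no longer be changed. If normality fails, use a rank-based or permutation version stratified by time since stroke in place of the plain rank sum test.

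**Cost.** A new list, a revised analysis paragraph, one or two degrees of freedom, and slight predictability at block ends, which varying the block size limits. No new measurement should be needed, because the 6-month limit cannot be applied without knowing disease duration.

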### **1 1. Intervention methods**

The control group received routine rehabilitation training: with the help of rehabilitation therapists, corresponding muscle strength training, comprehensive training of hemiplegic limbs, balance function training, limb neuromuscular electrical stimulation, acupuncture and other comprehensive rehabilitation treatments were carried out according to the patient's functional injury site. On this basis, the observation group added an EDP-D2 external diaphragm pacemaker (Zhongke Tyco (Guangzhou) Electronic Technology Co., Ltd.) for treatment. The specific operation steps are as follows: After

disinfecting the skin, place the small electrode pads on the lower 1/3 of the outer edge of the sternocleidomastoid muscles on the left and right sides, and place the large electrodes on the surface of the pectoralis major muscles on both sides, and fix them with medical tape. The pacing frequency and stimulation intensity are adjusted by the degree of stimulation. Each treatment time is 20 minutes, once a day, 5 days a week, and the treatment course is 4 weeks.

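### Section 10 says subjects did not know their group, but section 11 gives one arm alone a visible pacing device and describes no masking, so the statement is unsupported as written

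*Protocol*

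**What the plan says.** Protocol section 10 (Grouping method) describes allocation by a random number table and then states: "Subjects were randomly enrolled and were unaware of their grouping , and only some researchers were informed of the grouping".

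Section 11 (Intervention methods) defines the two arms. For controls: "The control group received routine rehabilitation training". The components listed include limb neuromuscular electrical stimulation and acupuncture. For the other arm: "On this basis, the observation group added an EDP-D2 external diaphragm pacemaker". Small pads go on both sides of the neck. For the chest, the instruction is to "place the large electrodes on the surface of the pectoralis major muscles on both sides, and fix them with medical tape". The schedule is: "Each treatment time is 20 minutes, once a day, 5 days a week, and the treatment course is 4 weeks".

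Section 12 (Measurement indicators) lists spirometry, standing and supine vital capacity, diaphragm ultrasound at quiet and deep breathing, and the mTIS scale, which rates "trunk balance ability before treatment and after 4 weeks of treatment".

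**The concern.** A patient can be kept unaware of the group only if the two arms look and feel alike to the patient, or if some other step hides the difference. Section 11 describes arms that differ in something the patient sees and feels, repeated over four weeks, and gives no means of hiding it. The sentence in section 10 therefore asserts a property that the described design does not deliver.

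What is at stake is how the results are read. A reader told that subjects did not know their group will discount patient expectation and effort as explanations for a difference between arms. Several outcomes are exposed to exactly those influences. The mTIS is the only measure of trunk balance, and trunk balance is the outcome named first in the aim (section 4). The treatment effect expected in section 15 covers both respiratory function and trunk balance, and each rests at least partly on tests that the patient performs.

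**Working it through.** The protocol gives no figure to reproduce here. The check sets the sections side by side, with one piece of arithmetic for the exposure.

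**1. What each arm receives (section 11).**
- Routine rehabilitation: both arms. It includes limb electrical stimulation.
- External diaphragm pacing with neck and chest electrodes: observation group only.
- Sham device, inactive stimulation, matched session or separation of patients: none described for either arm.

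**2. How much the arms differ (section 11).**
- Sessions: 5 days per week × 4 weeks = 20.
- Device time: 20 sessions × 20 minutes = 400 minutes.
- Described counterpart in the control arm: none.

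These figures give the difference in exposure. They do not measure how far blinding was lost.

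**3. Does the shared electrical stimulation mask the difference?** No. Limb stimulation belongs to routine care, which the observation group also receives. It is common to both arms and does not imitate electrodes on the neck and chest.

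**4. Could patients fail to notice?** Section 9 excludes people with severe cognitive impairment or abnormal hearing and understanding. Those enrolled can be expected to notice a taped device over 20 sessions. Whether they knew that the device defined the experimental group is not stated.

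**5. Which outcomes are open to expectation and effort (section 12)?**
- mTIS: the patient performs it. Section 9 already requires that "The patient can maintain the starting posture evaluated by the mTIS scale for 10 seconds".
- FVC, FEV1, and standing and supine vital capacity: all are voluntary breathing tests. FEV1/FVC and the percentage change in vital capacity are computed from them, so they cannot be presented as protected.
- Deep-breath excursion, described as "forced breathing diaphragm mobility (Diaphragmatic excursion of deep breath, DE-DB": it depends on how deeply the patient breathes.

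**6. Is masking described elsewhere?** None appears in the rest of the text shown. Section 5 (Design plan) is a heading with no extracted text, so a step shown only there cannot be excluded. Section 11, where the control treatment is defined, is readable and contains none.

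**The case against.** The strongest reply is that section 10 may not claim blinding at all. It uses neither 'blinded' nor 'masked', it sits under the allocation heading, and it reads like translated prose. It could mean only that patients were not told a group label, or did not know it when they enrolled. On that reading nothing in section 11 contradicts it. Electrical stimulation in both arms also makes it more plausible that a patient could receive pacing without knowing which component was under test. And no section calls the trial participant-blinded, so the misreading is a risk rather than a fact.

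Part of this stands. The narrow reading is possible, and it is why the sentence should be called unsupported rather than false. But the protocol does not say that this is what it means, and withholding a label does not establish blinding when only one arm receives the device. The reply therefore leads to a clarification and does not remove the need for one.

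A reader might infer stronger conclusions that the documents do not support:

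- *That the statement is proved false.* The protocol does not show what patients understood about the contrast. The consent pages are not available, and section 5 has no extracted text.
- *That the lack of a sham is itself a design error.* Comparing an added treatment with routine care alone is a legitimate choice. The problem is the statement attached to it.
- *That the assessors knew the grouping.* Section 10 says that some researchers were informed and does not say which. That is a missing detail and shows no fault.
- *That the results are biased by a known amount.* Nothing in the documents allows such a figure.

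**Conclusion.** The point holds in limited form: the statement that participants were unaware of their group is unsupported as written. In the text shown, one arm alone receives 20 sessions (400 minutes) of neck and chest pacing, and nothing is described that would hide this from patients.

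The consequence is interpretive. If no masking was used, differences in mTIS, spirometry, vital capacity and the values derived from them, and deep-breath diaphragm excursion cannot be read as free of patient expectation and effort. No direction or size of bias can be derived from the protocol.

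The conclusion assumes that section 11 is a full account of what each arm received and that no masking step stands only in the unextracted section 5. If one does, the remedy is to describe it in section 11. The matter should be fixed, because an unsupported claim of this kind changes how the main results are read and correcting it costs little.

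**What to change.** Reconcile sections 10 and 11 in one of three ways, according to what was done:

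1. If a masking step was used, describe it in section 11.
2. If none was used, replace the statement in section 10 with one that participants were not blinded.
3. If only the group label was withheld, say exactly that, and do not report the trial as participant-blinded.

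Absent masking, report the contrast as EDP plus routine rehabilitation versus routine rehabilitation alone, open to patients. Attach a caution about expectation and effort to mTIS, to spirometry and vital capacity with the values derived from them, and to deep-breath diaphragm excursion.

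This is a change of wording in the protocol and the report and needs no redesign. The downside is the loss of a favourable blinding claim. Expectation effects in measurements already made cannot be removed by rewording, only disclosed.
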